In Intensive Care Unit (ICU), the physiotherapist may be involved in the respiratory management of patients, notably with regard to lung aeration disorders, swallowing disorders, weaning from mechanical ventilation, aerosol therapy, oxygen therapy and the implementation of non-invasive ventilation (NIV), but this practice may vary internationally(1–3).

Chest physiotherapy techniques are selected following a systematic evaluation often based on clinical examination, review of measures of cardiopulmonary function/laboratory tests and review of any radiological tests. Evaluation of the patient is essential to determine the need for chest physiotherapy, treatment selection, monitoring the evolution of the patient and to evaluate treatment efficacy. Chest physiotherapy aims to improve airway clearance, alveolar recruitment and ventilation/perfusion matching (2). It typically involves techniques often used in combination (4), and the selection of interventions depends on the pulmonary dysfunction suspected. For example, in the case of retained airway secretions, airway clearance techniques (including patient re-positioning head down and manual chest wall vibrations/compressions and airway suctioning) may be used to promote secretion removal, reducing airway resistance, optimizing lung compliance and decreasing work of breathing (2). For lung collapse/consolidation, chest physiotherapy aims to improve lung recruitment, compliance and ventilation/perfusion matching. For example, positioning and lung hyperinflation may be used to re-expand atelectasis (2,5). Non-invasive ventilation, intrapulmonary percussive ventilation may be additional strategies optimise lung volume restoration and facilitate secretion clearance respectively (2,5,6).

Physiotherapist usually uses a clinical examination, including lung auscultation, and measures of physiological function including the analysis of blood gases and chest imaging findings (7). However, the reduced diagnostic accuracy of the chest x-ray and lung auscultation with regard to the conditions that may require chest physiotherapy such as pulmonary consolidation, pleural effusion, atelectasis or interstitial syndrome (8), implies that clinical decision-making may be less than optimal. Chest CT-scan is the gold-standard reference examination for the evaluation of acute lung injuries (9)but this requires transportation of the critically ill patient, which involves patient risk and additional exposure to radiation.

As an alternative to the CT-scan, lung ultrasound (LUS) presents greater sensitivity and specificity than chest X-ray in the diagnosis of these same diseases. LUS can also be used to assess the diaphragm with greater accuracy and reproducibility than is the case using routine

measurement tools which often provide only global measures of respiratory dysfunction (Maximal Inspiratory Pressure (MIP). Whereas, LUS can also be used to identify diaphragm dysfunction (both bilateral and unilateral dysfunction) with excellent sensitivity and specificity compared with standard of transdiaphragmatic measurements of pressure(10).

Physiotherapists working in critical care may be developing the skills to undertake LUS to assess their patients (9, 10). Lung and diaphragm US assessments may allow them to determine the optimal indications for chest physiotherapy and thus avoid unnecessary or inappropriate treatments (9, 10). The information provided by LUS may modify the physiotherapist's therapeutic management. Given the relatively recent discussions on the use of lung and diaphragm US in chest physiotherapy (11,12), the usefulness of this tool for physiotherapy in critical care has never been evaluated. Xirouchaki et al. (13)assessed the impact of LUS on clinical decisions in critically-ill patients by intensivists and demonstrated that it significantly affected the medical diagnosis and modified the therapeutic management. Also a recent case report highlighted the impact of LUS on the clinical decision-making by physiotherapists in critical care (14). As far as we are aware, no study has prospectively and systematically evaluated the impact of the information provided by LUS on clinical-decision making by physiotherapists in the use of chest physiotherapy in patients hospitalized in an ICU.

2. Researchhypothesis

The lung and diaphragm ultrasound findings provided to the physiotherapist will modify his/her clinical decision-making in regards to chest physiotherapy treatment in the critical care patient.

3. Objectives

3.1.Principal objective

The principal objective of this study is to evaluate the impact of using the results of lung and diaphragm US on clinical decisions by physiotherapists regarding chest physiotherapy in patients hospitalized in an ICU.

3.2.Secondary objectives

The secondary objectives are to:

1. Determine whether LUS has an impact on clinical decisions in chest physiotherapy:
 - When the findings from a chest CT-scan less than 12hours old are available;
 - For each clinical hypotheses;
 - For each level of certainty of clinical hypothesis;
 - For type of patients (reasons for admission the most represented);
 - For each research center.
2. Determine the level of agreement between the physiotherapist's diagnosis comparing the clinical vs LUS findings, overall, for the level of certainty of clinical diagnosis and for the population where a CT-scan is available;
3. Determine the frequency of changes in the chest physiotherapy following the assessment of the LUS results, overall and for each type of clinical hypothesis;
4. Determine the frequency of changes in the medical treatment (determined by intensivist) following the assessment of the LUS results performed by the physiotherapist, overall and for each type of clinical hypothesis.

4. Judgement criteria

4.1.Principal judgement criterion

Modification of the clinical decision: agreement (yes/no) between the lung and diaphragm US diagnosis and the clinical diagnosis and modification (yes/no) of the chest physiotherapy protocol, expressed using the Net Reclassification Index (NRI).

4.2.Secondary clinical decision-makingjudgementcriteria

1. Modification of the clinical decision:
 - When a chest CT-scan < 12h is available;
 - For each clinical hypotheses;
 - For the level of certainty of clinical hypotheses (Likert scale: strongly certain, certain, neither certain nor uncertain, uncertain, strongly uncertain);

- For type of patients (reasons for admission the most represented);
 - For each research center.
2. Proportion of agreement between clinical and LUS diagnosis:
- Overall;
 - For the level of certainty of clinical hypotheses (Likert scale: strongly certain, certain, neither certain nor uncertain, uncertain, strongly uncertain);
 - When chest CT-scan < 12h is available.
3. Proportion of cases when the chest physiotherapy protocol is modified following the results of the LUS:
- Overall;
 - For each type of clinical hypothesis;
 - When a chest CT-scan < 12h is available;
4. Modification of the clinical decision of intensivist:
- Overall;
 - For each type of clinical hypothesis;
 - When a chest CT-scan < 12h is available.

5. Inclusion/exclusion criteria:

5.1. Inclusion criteria

Patients presenting the following criteria will be eligible:

- Hypoxemia ($SpO_2/FiO_2 < 315$ (15)) (indication for chest physiotherapy) (*cf. annexe 1*);
- Medical prescription for chest physiotherapy;
- First session of chest physiotherapy;
- Chest X-ray < 12h available;
- Physiotherapist/operator qualified in LUS available;
- Patient's consent.

5.2.Exclusion criteria

Patients presenting the following criteria will not be eligible:

[figure not shown]
- Presence of a contra-indication for chest physiotherapy;
- Absence of hypoxemia;
- Absence of a prescription for chest physiotherapy;
- Absence of a chest X-ray < 12h from the time of physiotherapy assessment;
- Physiotherapist/operator qualified in LUS not available;
- Lung and diaphragm US not possible (surgical emphysema, dressing, scarring, drains etc.);
- Refusal of the patient or a relative to participate in the study;
- Patients to be discharged on the day of the study;
- Patients in palliative care;
- Withdrawal/limitations of medical care with impending death.

6. Methodology:

6.1.Type of study

This is a multi-centre prospective (patients enrolled on admission) interventional study evaluating a routine assessment/treatment. The study intends to assess the impact of lung and diaphragm ultrasound on the usual physiotherapist's clinical decision-making process. Each included patient will be clinically assessed by a clinical physiotherapist, and then will have a lung and diaphragm ultrasound by another physiotherapist/operator blinded to the clinical assessment findings. The lung and diaphragm ultrasound findings will then be presented to both the intensivist and clinical physiotherapist to evaluate the impact on the independent clinical decision-making by both the intensivist and physiotherapist.

6.4. Study population

Patients over 18 hospitalized in the ICU and presenting hypoxemia ($SpO_2/FiO_2 < 315$) and who have not been previously given chest physiotherapy on this ICU admission.

6.5. Intervention: nature of the routine care to be evaluated

6.5.1. Procedure 1: Decision-making process in chest physiotherapy

6.5.1.1. *Clinical physiotherapist training*

The clinical physiotherapist is the physiotherapist who manages patients in the ICU. He is a trained critical care physiotherapist with more than two years of experience, as defined by the French statement for physiotherapist working in the French ICU’s(1). The clinical physiotherapist in the Australian ICU will have been trained and oriented to working in the ICU based on a local structured training program dependent on the level of experience of the physiotherapist.

6.5.1.2. *Indication and prescription of chest physiotherapy*

In the French ICU departments, the intensivist prescribes chest physiotherapy for patients, whereas in the Australian setting, the physiotherapist screens all patients admitted to intensive care and provides interventions based on clinical need. All patients with hypoxemia ($SpO_2/FiO_2 < 315$) will result in referrals for chest physiotherapy by the intensivists in the French ICU(5). All patients with hypoxemia ($SpO_2/FiO_2 < 315$) will be reviewed by the physiotherapists in the Australian ICU as to the requirements for physiotherapy.

6.5.1.3. *Clinical examination*

When chest physiotherapy is prescribed by the intensivist in the French ICU (or the patient has indications for chest physiotherapy in the Australian ICU as stated 6.5.1.2), the clinical physiotherapist carries out a clinical examination and will analyse the complementary tests (chest X-ray, chest CT-scan and blood gases if available). He/she also consults the patient’s medical record to identify reasons for admission to the ICU and the working medical diagnosis if the critical care physician has made one.

The physiotherapists' clinical examination includes:

- Patient observation:
 - Thoracic cage observation: asymmetry of chest wall movement, hyperinflation etc.
 - Respiratory breathing pattern: respiratory rate, dyspnoea, tachypnoea, bradypnoea, Hoover sign, Campbell sign, respiratory pattern (thoracic expansion, abdominal expansion, paradoxical chest or abdominal movement);
 - Physiologic data: SpO₂, heart rate, blood pressure;
- Chest wall palpation: vocal fremitus, tactile chest wall fremitus, subcutaneous emphysema;
- Chest wall percussion: dullness or tympanism;
- Lung Auscultation:
 - Normal breath sound: vesicular sound, bronchial sound;
 - Abnormal sound: crackles, rhonchi, wheeze etc.

Then, the physiotherapist interprets the additional tests:

- Chest X-rays: opacities, consolidation, volume loss, bronchogram, pneumothorax, pulmonary oedema;
- Chest CT-scan (if available): opacities, emphysema pneumothorax, pulmonary oedema;
- Arterial blood gas: hypoxemia (PaO₂<75-80 mmHg), hypercapnia (PCO₂> 45 mmHg), acidosis (pH <7,30), alkalosis (pH >7,44).

After the analysis of the clinical examination findings, the physiotherapist then determines one or several working clinical hypothesis.

6.5.1.4. Clinical hypotheses

Following the examination, he/she will put forward one or several hypotheses concerning the respiratory dysfunction (and not the medical diagnosis) and will either confirm or refute the indications for chest physiotherapy (*cf. annexe 2a*). If chest physiotherapy is indicated, the physiotherapist will specify the protocol to be used. The choice of the treatment modalities with regard to the type of respiratory dysfunction is detailed in annexe 2b.

According to the clinical examination, the clinical physiotherapist formulates one or more of the following clinical hypothesis (*cf annexe 2a*):

- Clinical examination is compatible with retained airway secretions;
- Clinical examination is compatible with bronchospasm;

- Clinical examination is compatible with pneumonia/consolidation;
- Clinical examination is compatible with atelectasis (~~passive or obstructive~~active mechanism);
-
- Clinical examination is compatible with pleural effusion;
- Clinical examination is compatible with pulmonary edema or global interstitial syndrome;
- Clinical examination is compatible with pneumothorax;
- Clinical examination is compatible with reduced aeration at the most dependent parts of the lungs;
- Clinical examination is compatible with unilateral diaphragm dysfunction (~~unilateral or bilateral~~);
- Clinical examination is compatible with bilateral diaphragm dysfunction;
- Clinical examination is inconclusive.

Among the formulated clinical hypotheses, the clinical physiotherapist will choose one primary clinical hypothesis (the choice is left to the discretion of the clinical physiotherapist, based on the probability and priority of the clinical hypothesis in terms of treatment).

A lung and diaphragm US will be done (see below) following the evaluation of the clinical physiotherapist with the physiotherapist who undertakes the US assessment blinded to the clinical assessment findings of the clinical physiotherapist. The clinical physiotherapist will then incorporate the results of the lung and diaphragm US and deem whether they are compatible with the clinical hypotheses put forward. He/she will then specify the chest physiotherapy protocol according to the results of the US-scan.

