8.2. Statistical method

8.2.1. Modification of the clinical decision chest physiotherapy

Calculation of the net reclassification index (NRI) (29):

$$\text{NRI (\%)} = (P_{\text{upevents}} - P_{\text{downevents}}) - (P_{\text{upnonevents}} - P_{\text{downnonevents}})$$

With:

Events: the results of the lung and diaphragm US are compatible with the clinical diagnosis for a clinical hypothesis.

Non Events: the results of the lung and diaphragm US are not compatible with the clinical diagnosis for a clinical hypothesis.

P_{upevents}: number of «events» when the LUS results modified the chest physiotherapy treatment modalities divided by the total number of «events».

P_{downevents}: number of «events» when the LUS results didn't modify the chest physiotherapy treatment modalities divided by the total number of «events».

P_{upnonevents}: number of «non-events» when the LUS results modified the chest physiotherapy treatment modalities divided by the total number of «non-events».

P_{downnonevents}: number of «non-events» when the LUS results didn't modify the chest physiotherapy treatment modalities divided by the total number of «non-events».

The significance test used will be the correlated proportions test (use of the properties of multinomial distribution). This is an asymptotic test for the hypothesis $NRI=0$.

$$z = \frac{\widehat{NRI}}{\sqrt{\frac{\hat{p}_{up,events} + \hat{p}_{down,events}}{\# \text{ events}} + \frac{\hat{p}_{up,nonevents} + \hat{p}_{down,nonevents}}{\# \text{ nonevents}}}}$$

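### The primary index has no stated rule for event status, and the only text naming a judge points to the physiotherapist who then sets treatment

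*Combined protocol and SAP*

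**What the plan says.** Section 4.1 makes the primary criterion "agreement (yes/no) between the lung and diaphragm US diagnosis and the clinical diagnosis and modification (yes/no) of the chest physiotherapy protocol", summarised as a net reclassification index. Section 8.2.1 defines an event as a case in which "the results of the lung and diaphragm US are compatible with the clinical diagnosis for a clinical hypothesis". A non-event is the opposite. Within each class, P_up is the proportion whose treatment modalities were modified and P_down the proportion whose modalities were not. Neither section says who decides compatibility or by what rule.

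Section 6.5.1.4 is the only place that assigns the judgement. The clinical physiotherapist forms one or more hypotheses and picks a primary one; "the choice is left to the discretion of the clinical physiotherapist, based on the probability and priority of the clinical hypothesis in terms of treatment". After the scan, the same person is to take in the ultrasound results and "deem whether they are compatible with the clinical hypotheses put forward". The next sentence reads: "He/she will then specify the chest physiotherapy protocol according to the results of the US-scan".

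What is recorded is set out in sections 7.4.3 to 7.4.5: the pre-scan primary and secondary hypotheses, the pre-scan treatment choice, the operator's ultrasound diagnosis or diagnoses, and the second treatment choice with reasons for any change. A compatibility verdict is not listed there or in the schedule in 7.4.8. That schedule does tick the clinical hypotheses a second time, when the scan results are read.

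**The concern.** Event status is the grouping variable of the primary index and treatment modification is its outcome. If the bedside judgement in 6.5.1.4 supplies event status, both come from one person, who knows the scan result, in consecutive steps. In a borderline case, someone inclined to keep the plan may lean towards calling the scan compatible, and someone inclined to change it may lean the other way. Part of the association would then be made by the labelling.

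There is room for discretion. Several hypotheses and several ultrasound diagnoses are allowed per patient. Section 6.5.1.4 compares the scan with the hypotheses in the plural, 8.2.1 with a single hypothesis, and section 6.5.1.5 sets treatment for the primary hypothesis. Section 6.5.2.3 links one pattern to several conditions: focal interstitial syndrome fits pneumonia, atelectasis or contusion. It also says that a normal profile fits retained secretions and bronchospasm, but not whether an abnormal profile counts against them.

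At stake is whether the primary result can be reproduced from the recorded data and read as an effect of the scan information.

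**Working it through.** **1. Who assigns event status?**
- 4.1: agreement between the two diagnoses; no rater, no rule.
- 8.2.1: compatible or not; no rater, no rule.
- 6.5.1.4: the clinical physiotherapist judges compatibility, then specifies treatment.
- 6.5.2.1 and 7.4.4: only the ultrasound operator is blinded.
- 6.5.2.4: the referent intensivist validates the ultrasound report, for French operators only. This does not cover compatibility.
- 8.2.3: the T1-T8 table serves kappa and leaves out retained secretions and bronchospasm.

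**2. What the index reduces to.** Within each class P_down = 1 - P_up. With a and b the modified proportions among events and non-events:

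Index = (2a - 1) - (2b - 1) = 2(a - b)

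The numerators under the root in the stated z each sum to 1, so SE = sqrt(1/#events + 1/#nonevents).

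**3. Inputs.** Section 8.1 gives 150 patients, at least 50 modifications and an expected index of 30%. These do not reproduce one another exactly (50/0.30 = 166.7; 150 x 0.30 = 45). That is a separate matter, and here 150 and 50 serve only as fixed totals. The documents give no split between events and non-events, so every split and every number of relabelled patients below is an assumption.

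**4. Same patients and same treatment decisions; only the compatibility label changes.**

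| Labelling | Modified, compatible | Modified, not compatible | Index | z |
|---|---|---|---|---|
| Starting point | 19/75 | 31/75 | 2(0.2533 - 0.4133) = -32.0% | -1.96 |
| 5 modified moved to not compatible | 14/70 | 36/80 | 2(0.2000 - 0.4500) = -50.0% | -3.06 |
| 5 modified moved to compatible | 24/80 | 26/70 | 2(0.3000 - 0.3714) = -14.3% | -0.87 |
| 5 unmodified moved to compatible | 19/80 | 31/70 | 2(0.2375 - 0.4429) = -41.1% | -2.51 |
| 5 unmodified moved to not compatible | 19/70 | 31/80 | 2(0.2714 - 0.3875) = -23.2% | -1.42 |

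Modified patients total 50 of 150 in every row.

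**5. No association at the start.** With 25/75 modified in each class the index is 0. Moving ten modified patients from compatible to not compatible gives 15/65 against 35/85: 2(0.2308 - 0.4118) = -36.2%, z = -2.20.

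**6. Other splits.** Over assumed splits from 60/90 to 120/30, relabelling five modified patients (5/150 = 3.3%) moves the index by 17 to 27 points.
- Smallest shift, 90/60 with 25 and 25 modified: from -27.8% to 2(20/85 - 30/65) = -45.2%.
- Largest shift, 120/30 with 36 and 14 modified: from -33.3% to 2(41/125 - 9/25) = -6.4%.

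Under the definitions in 8.2.1, more modification when the scan disagrees makes the index negative. The expected 30% in 8.1 is therefore a yardstick for size here, not for sign.

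**The case against.** The strongest reply is that the rater is inferred. Section 6.5.1.4 may describe only bedside reasoning. Section 4.1 speaks of agreement between two diagnoses, both are recorded, and no verdict is listed for recording, so the analyst may have been meant to derive agreement. This stands as far as it goes: the documents do not establish that the physiotherapist's verdict is the analysis variable. But no derivation rule is written either, so that reading needs the same addition to the plan.

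Discretion is also limited. The hypothesis is recorded before the scan, the operator is blinded, and Annexe 2b ties treatment to hypothesis. Section 6.5.1.4 places the judgement before the treatment choice, and some association between disagreement and treatment change is what the study expects to see. The clinical physiotherapist must see the report in order to revise treatment, so knowledge of the scan is not in itself a fault. All of this stands. It confines the problem to ambiguous or multiple-finding cases, whose number is unknown.

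A reader might infer two stronger points that the documents do not support.
- *An examination recorded as "Clinical examination is inconclusive" can never count as compatible.* Annexe 4 offers a no-conclusion result, and T8 sits on both axes of the table in 8.2.3, so a match is possible. What is missing is how the primary index treats it.
- *Self-confirmation inflates the planned agreement statistics.* Observed agreement and kappa in 8.2.3 come from cross-tabulating the diagnoses T1-T8. Changing a bedside compatibility verdict leaves that table as it is.

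**Conclusion.** The concern holds as a gap in the definition of the primary variable that opens a route to bias. It is not a demonstrated bias. If 6.5.1.4 is followed as written, one person supplies both grouping and outcome; if it is not, nothing says what replaces it. On the assumed 75/75 split, relabelling five modified patients moves the index from -32% to -50% or to -14%. Across the splits tried the shift is 17 to 27 points, against an expected index of 30%. The sensitivity follows from the formula; the counts are illustrative.

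A reader might conclude that the index is biased in a particular direction, for instance away from zero. The documents do not support that, because relabelling can enlarge or shrink the index, and how often labels would be discretionary is unknown. The change below is a cheap improvement that should be made.

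**What to change.** In 8.2.1, state that event status is derived at analysis from two recorded items: the pre-scan primary clinical hypothesis (7.4.3) and the blinded operator's Annexe 4 diagnosis or diagnoses (7.4.4). Specify the pre-scan entry, because the schedule in 7.4.8 ticks the hypotheses again after the scan is read.

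Attach a table, fixed before data review, that marks each pair of clinical hypothesis and ultrasound diagnosis as compatible, not compatible or not testable, building on 6.5.2.3. Add:
- a rule for several ultrasound diagnoses, for example compatible if any recorded diagnosis matches the primary hypothesis;
- a separate class for inconclusive examinations, with its handling in the index stated;
- the physiotherapist's own compatibility judgement as a secondary description, if it is collected.

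The primary analysis needs no new data, no extra assessor and no change to care. The cost is one table and the discussion to agree it, mainly on patterns that fit several conditions. The drawback is that a fixed table is less flexible than bedside judgement.
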